10.2 Secondary Efficacy Outcomes

All secondary efficacy outcomes will be summarized by descriptive statistics using the MITT Population except that the bleeding and/or spotting analyses will be summarized using both Safety and MITT Populations. Additional summaries will be provided for the median MBL change from baseline to End-of-study for subgroups such as age (18 to ≤ 35 and ≥ 36 yo), race/ethnicity, and BMI (<25 , 25 to <30 , or ≥ 30).

11. SAFETY ANALYSIS

All safety analyses will be based on the Safety population.

11.1 Adverse Events

Menstrual bleeding and cramping/pain are recorded in a daily subject diary and not on the Adverse Events CRF. The subject daily diary has been designed to collect IUS and menstrual bleeding and cramping AEs following insertion of the study IUS. Menstrual bleeding or cramping/pain would only be entered onto the general AE CRF if:

- Bleeding or cramping/pain meet serious criteria; an SAE report would also have to be submitted (this exception is due to data system requirements)
- Bleeding or cramping/pain result in the IUS being removed (this exception is due to data system requirements)

- Bleeding or cramping/pain is not related to the IUS or a menstrual condition

All adverse event summaries will be restricted to treatment-emergent adverse events (TEAE), defined as AEs occurring during or after attempted IUS insertion and those pre-attempted IUS insertion existing medical conditions that worsened during the study up to the subject's last known IUS date of use or, for subjects who have discontinued, through the safety contact after the subject's last known IUS date of use. If an AE cannot be determined as treatment-emergent, it will be counted as such.

Verbatim terms on case report forms will be mapped to preferred terms and system organ classes using the Medical Dictionary for Regulatory Activities (MedDRA) dictionary. Each adverse event summary will be displayed by treatment group. Summaries that are displayed by system organ class and preferred terms will be ordered by descending order of incidence of system organ class and preferred term within each system organ class. Summaries of the following types will be presented:

- Overall subject summary of AEs, SAEs, and deaths
- Subject incidence of TEAEs and total number of unique TEAEs by MedDRA system organ class and preferred term.
- Subject incidence of TEAEs by MedDRA system organ class, preferred term, and highest severity. At each level of subject summarization a subject is classified according to the highest severity if the subject reported one or more events. AEs with missing severity will be considered severe for this summary
- Subject incidence of TEAEs by MedDRA system organ class, preferred term, and closest relationship to IUS (Related/Not Related). At each level of subject summarization a subject is classified according to the closest relationship if the subject reported one or more events. Related will be defined as “Related”, “Probably Related”, or missing. Not related will be defined as “Unlikely Related” or “Not Related”. All adverse events will be summarized with special attention to those events that may be related to an IUS, including:
 - Uterine perforation;
 - Low abdominal pain (not classified as dysmenorrhea or related to insertion/removal);
 - Pelvic infection (including uterine infection, PID and endometritis); and
 - Other urogenital infections
- Subject incidence of TEAEs by MedDRA system organ class, preferred term, and closest relationship to IUS Procedure (Related/Not Related). At each level of

subject summarization a subject is classified according to the closest relationship if the subject reported one or more events. Related will be defined as “Related”, “Probably Related”, or missing. Not related will be defined as “Unlikely Related” or “Not Related”

- Subject incidence of serious TEAEs and total number of unique serious TEAEs by MedDRA system organ class and preferred term

Incidence rates will include in the denominator all subjects in the Safety Population.

Missing Severity or Relationship

Missing severity or relationship to study drug will prompt queries to be sent to the investigators to provide the information. If after query resolution, the information remains missing, the following conventions will be used in summary tables.

- An event with missing severity will be considered Severe.
- An event with missing relationship will be considered related to study drug.

11.2 Insertion and Removal Related Bleeding and Cramping/Pain

IUS insertion and removal bleeding and cramping/pain related to IUS insertion and removal will be summarized for treatment group. IUS insertion related bleeding and cramping/pain are recorded on the IUS Insertion Questionnaire. IUS removal related bleeding and cramping/pain are recorded on the IUS Removal Questionnaire.

Summaries of the following will be presented:

- Bleeding (none, spotting, light bleeding, moderate bleeding, heavy bleeding)
- Cramping/pain (none, mild, moderate, severe)

11.3 Menstrual Related Cramping/Pain

A subject will be defined as having menstrual cramping/pain (dysmenorrhea) TEAE if the subject diary question, “Check box if cramping today is more severe than your normal worst cramping” is marked.

Subject incidence of cramping/pain or dysmenorrhea TEAEs will be described within the overall adverse event incidence summary.

Dysmenorrhea (none, mild, moderate, or severe) will be summarized by the number and percentage of days with a particular pattern during each 28-Day interval after enrollment through end of Cycle 6 or IUS Discontinuation. In addition, dysmenorrhea changes from baseline (as established by the worst cramping during the screening cycles) will be summarized using shift tables.

For each 28-day cycle the incidence of on-treatment cramping/pain (none, mild, moderate, severe) will be calculated based on diary entries and presented by treatment group. Summaries of the following types will be presented:

- Incidence of cramping/pain by 28-day cycle intervals post-insertion (none vs. ≥ 1 day; 1-3, 4-7, >7 , and >20 days)
- Incidence of cramping/pain by highest severity by cycle intervals post-insertion. At each level of subject summarization a subject is classified according to the highest severity or intensity if the subject reported one or more events.

Descriptive continuous-based statistics (mean, standard deviation, median, minimum, maximum) will be used to summarize the number of days of reported cramping and during each 28-day cycle. For cramping/pain, this will also be presented within each severity rating, i.e., the total number of reported days will be broken down into the number of days of mild, moderate, and severe cramping/pain.

11.4 Menstrual Related Bleeding

A subject will be defined as having a menstrual Bleeding TEAE if the subject diary question, “Check box if bleeding today is more severe than your normal heaviest flow” is marked.

Subject incidence of bleeding TEAEs will be described within the overall adverse event incidence summary.

11.5 Insertion

The number and percentage of subjects with a successful insertion and where rigid cervical dilation or local anesthesia was used. The distribution of easy, neutral, or difficult insertions will be summarized by insertion attempt.

Summaries will also be presented for other inserter-related outcomes, such as the number and percentage of subjects where insertion failure occurred, difficulty of insertion, use of cervical dilation, perforation, expulsion, and insertion-related bleeding and cramping.

Some subjects will meet the protocol defined IUS insertion failure, which is when, after advancing through the external cervical os by the inserter, completion of IUS insertion is not achieved. However, some of these insertion failures are unrelated to the study IUS or inserter and such cases will not be analyzed as insertion failures. Examples of such situations include, but are not limited to:

- withdrawal of consent after enrollment and before IUS placement
- cervix could not be visualized
- inserter became contaminated
- subject could not tolerate sounding
- uterus could not be sounded
- uterus sounded to < 5.5 cm
- enrolled but determined not to be eligible before IUS placement

Subjects who had a failed first insertion but never came back for a second attempt are considered to be a failed insertion and not a discontinuation due to withdrawal of consent or lost to follow-up.

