6.6 IUS Insertion Definitions

Up to two insertion attempts are permitted.

- An **insertion attempt** starts with placement of the IUS inserter through the external cervical os. IUS insertion ends with completion of cutting the IUS threads following successful intrauterine IUS placement or IUS insertion failure.
 - **IUS insertion failure** is considered to occur when after the IUS inserter passes through the external os of the cervix and completion of IUS insertion is not achieved.
 - **Successful IUS insertion** is considered as retention of the IUS in the uterus through cutting of the strings, unless removed for incorrect placement as determined by ultrasound or other means within the duration of the same clinic visit; the day of successful IUS insertion is considered Study Day 1.

- Note that **IUS insertion** is the general process that starts with opening of the LNG20 IUS kit with the intent to perform an insertion. The insertion process may stop before IUS insertion is attempted (see definition above); in such circumstances, an IUS insertion attempt has not occurred. Examples of procedure discontinuation prior to an insertion attempt include:
 - notable defect upon inspection of the product
 - loss of product sterility
 - inability to sound the uterus
 - subject intolerance of the procedure prior to LNG20 IUS contact with the external cervical os

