18. APPENDIX G: MANAGEMENT OF IUS ISSUES

1. Difficult Insertion

If insertion is difficult because the cervix cannot be properly visualized then the subject should have been excluded prior to randomization.

- If insertion is difficult because the uterus cannot be instrumented, the following measures are allowed:
 - Use of cervical anesthesia to make sounding and manipulation more tolerable
 - Use of rigid dilators to dilate the cervix if needed to allow passage of the sound.
If needed, a lacrimal duct probe or os finder may be used to start dilation.
 - Abdominal ultrasound guidance during dilation and/or insertion.

If the uterus still cannot be appropriately instrumented after the above measures are taken, or the uterus sounds to less than 5.5cm, then the subject should be considered an insertion failure and discontinued from the study. No further follow-up or visits are required.

2. Perforation

- Perforation may occur during insertion. The risk of perforation is increased in women with fixed retroverted uteri, during lactation, and postpartum. If during or after insertion there is clinical concern or exceptional pain or bleeding, appropriate and timely measures and assessments, such as ultrasound, should be performed to exclude perforation.
- Perforation or penetration of the uterine wall or cervix may occur during insertion although the perforation may not be detected until sometime later. The IUS must be located and removed; surgery may be required. Delayed detection of perforation may result in migration outside the uterine cavity, adhesions, peritonitis, intestinal perforations, intestinal obstruction, abscesses and erosion of adjacent viscera. Ensure a radiographic image of the entire abdomen is obtained to ensure the IUS hasn't migrated.
- If recognized and the IUS is intra-abdominal, a laparoscopy should be performed by a clinician experienced in such procedures to remove the IUS. Typically, minimal adhesions are present with intra-abdominal IUSs. If necessary, a laparotomy should be performed.

If the IUS is partially into or through the myometrium, it is reasonable to attempt removal with transcervical instrumentation. Initial attempts should be performed under ultrasound

guidance using an Alligator forceps (or similar instrument). If unsuccessful, attempts via hysteroscopy should be made before proceeding to laparoscopy.

3. Missing Strings

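### Protocol 6.6, Protocol Appendix G and SAP 11.5 define insertion failure inconsistently, and SAP 11.5 lets failures that meet the protocol definition be removed under an open-ended list

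*SAP*

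**What the plan says.** Three passages bear on what counts as an insertion failure.

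- **Protocol 6.6** gives the formal definition. A failure occurs when "after the IUS inserter passes through the external os of the cervix and completion of IUS insertion is not achieved". If the process stops earlier, no attempt has taken place. Its examples of an early stop include inability to sound the uterus, loss of sterility, and intolerance before the device touches the os.
- **Protocol Appendix G, item 1 (Difficult Insertion)** covers a uterus that still cannot be instrumented after the permitted measures, "or the uterus sounds to less than 5.5cm, then the subject should be considered an insertion failure and discontinued from the study".
- **SAP 11.5** repeats the 6.6 definition and then says: "However, some of these insertion failures are unrelated to the study IUS or inserter and such cases will not be analyzed as insertion failures". It introduces seven situations with "Examples of such situations include, but are not limited to"; two of them are "uterus could not be sounded" and "uterus sounded to < 5.5 cm". Its last sentence classes a woman whose first insertion failed and who did not return as a failed insertion, and expressly not as a withdrawal of consent or a loss to follow-up.

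SAP section 1 gives the SAP precedence over the protocol where the two differ on analysis. SAP 11.5 does not name a denominator for the failure percentage.

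**The concern.** Whether the device can be placed is a safety and usability result in its own right. The study is single-arm and open-label, so whoever decides that a failure had nothing to do with the device knows both the device and the outcome. The SAP gives no criterion for that decision, names nobody to make it and sets no time by which it must be made.

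A site following Appendix G may record a failure that the analysis then leaves out. Two analysts could report different failure rates from the same records and each cite a passage in support.

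**Working it through.** The documents give no expected, planned or threshold insertion-failure rate, so there is no figure to reproduce. The check is mainly a comparison of text.

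**Step 1. The seven SAP 11.5 examples against the two protocol passages.**

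| SAP 11.5 example | Protocol 6.6 | Appendix G |
|---|---|---|
| Consent withdrawn between enrollment and placement | Depends on when enrollment occurs (step 2) | Silent |
| Cervix not visualized | Before the os, so no attempt | Should have been excluded earlier; not called a failure |
| Inserter contaminated | Loss of sterility is listed as a stop before an attempt | Silent |
| Sounding not tolerated | Intolerance before os contact is listed as a stop before an attempt | Arguably a failure (cannot be instrumented) |
| Uterus could not be sounded | Listed as a stop before an attempt | Failure |
| Sounded below 5.5 cm | Not named; sounding precedes the inserter, so no attempt | Failure |
| Enrolled, then found ineligible before placement | Depends on when enrollment occurs | Silent |

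Five of the seven arise before the inserter passes the os, and the other two depend on timing. SAP 11.5 nevertheless presents them as examples of failures that occurred after that point. Appendix G overlaps two of the seven explicitly and a third arguably.

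**Step 2. What the removal does to true 6.6 failures.** Under 6.6, the five pre-os cases are not failures and need no rule to remove them. The rule changes a 6.6 count only for failures after the os. Consent withdrawal is one route. Protocol 6.8 says an insertion attempt enrolls the woman, so on that reading a withdrawal after enrollment and before placement follows an attempt. (Protocol 4.1 instead dates enrollment from the start of the insertion procedure.) The open-ended wording is the other route.

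**Step 3. Conflict within SAP 11.5.** Take a woman whose first attempt fails and who then withdraws consent. The first example removes her from the failures. The last sentence of the section counts her as a failure.

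**Step 4. Denominator.** The protocol's Safety population (9.2) is women who underwent the insertion procedure, and under 6.6 that process starts when the kit is opened. The SAP's Safety population (section 6) requires an insertion attempt. A woman who could not be sounded is in the first and, by 6.6, not in the second.

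**Step 5. Size, for illustration only.** Assume N = 100 women, f = 2 counted failures and k removed cases. Only the planned enrollment of about 100 comes from the documents; f and k are assumptions.

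- Removed cases counted: (f + k)/N
- Removed cases kept in the denominator only: f/N
- Removed cases dropped from both: f/(N − k)

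| k | Counted | Denominator only | Dropped from both |
|---|---|---|---|
| 0 | 2.0% | 2.0% | 2.00% |
| 1 | 3.0% | 2.0% | 2/99 = 2.02% |
| 2 | 4.0% | 2.0% | 2/98 = 2.04% |
| 5 | 7.0% | 2.0% | 2/95 = 2.11% |

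A woman with a true 6.6 failure has had an attempt and belongs in the denominator, so each removal lowers the rate by 1/100 = 1.0 point. For pre-os cases, the first two columns apply if Appendix G is the reference and all women stay in the denominator. The third column applies under 6.6 with the SAP Safety population, where these women are neither failures nor in the denominator. The Clopper-Pearson 95% intervals are 0.2–7.0% for 2/100 and 1.1–9.9% for 4/100, so differences of this size are small beside the sampling error.

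**The case against.** A reader might infer that the reported failure rate is too low because the SAP drops several cases that the protocol counts. The documents do not support that reading. The formal definition is in 6.6, and it treats inability to sound as no attempt, so leaving those women out agrees with 6.6. The contradiction over them lies inside the protocol, between 6.6 and a management appendix. Sounding below 5.5 cm is also a failure of inclusion criterion 8, and Protocol 6.8.2 lists it as an alternative to two unsuccessful attempts. The overlap with Appendix G is two examples, or three at most.

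Much of the all-cause picture is already planned. SAP 11.5 reports the percentage with successful insertion. SAP 7.1 tabulates successful insertions by attempt, discontinuations after failed insertion, and reasons for discontinuation. The rule for women who do not return raises the count. Separating patient-side reasons from device reasons is sensible in a section on inserter-related outcomes. Insertion failure is not among the outcomes listed in Protocol 3.1 and has no threshold.

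All of this stands, and it limits the point. It does not justify removing a failure that meets 6.6, and it does not resolve the conflict within SAP 11.5. SAP 7.1 does not say which definition of failed insertion it uses, so its table may not settle the count.

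**Conclusion.** The point holds as an inconsistency of definition with one established direction. Where a woman's failure meets Protocol 6.6, removing her as unrelated can only lower the reported rate, by about 1 percentage point per woman if about 100 women have an attempt. For women stopped before the os, the effect runs from nothing, under 6.6 with the SAP denominator, to about 1 point per woman, under Appendix G with all women kept in. The documents give no count from which to size the total, and no downward bias is shown for those cases.

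The outcome is descriptive. The primary endpoint is unaffected, because the MITT population already requires a successful insertion. The change should be made because the rate cannot be reproduced as specified and the correction is cheap.

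**What to change.** 1. Reconcile Protocol 6.6, Protocol Appendix G and SAP 11.5 so that each pre-os situation has one stated classification for analysis.
2. In SAP 11.5, delete the clause that takes unrelated cases out of the analysis.
3. Report two rates side by side: all failures meeting Protocol 6.6 over women with an insertion attempt, and all-cause non-placement over all women in whom the insertion procedure was started. Name both denominators in the SAP.
4. Show reasons as a breakdown. Keep failures not attributable to the device or inserter as a secondary row, using a closed list fixed before database lock.
5. State which rule governs a woman who withdraws consent after a failed first attempt, and use the same definition in the SAP 7.1 disposition table.

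The cost is wording and an extra table row or two. The reported failure rate may be slightly higher.

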11.6 Continuation, Expulsion, and Removal Rates

Cumulative rates of IUS continuation, expulsion, and safety-related removal at 1 month (Visit 6), 3 months (Visit 7) and 6 months (Visit 8) will be summarized and analyzed using Kaplan-Meier methods. Time to event will be calculated as the date of continuation/expulsion/removal minus the date of IUS insertion plus one. Subjects without a continuation/expulsion/removal will be censored at the last contact date (as described in [Section 5.4](#)) and failure time will be calculated as the last contact date minus the date of IUS insertion plus one. Subjects who report an expulsion that is not confirmed by the study site will be censored. The safety-related removal rates may also be summarized by MedDRA preferred term in the same manner. Expulsion rates including analysis of complete and partial expulsions in the Safety Population will also be summarized.

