5.4 IUS Replacement

Subjects experiencing an expulsion (complete or partial) may have another study IUS inserted; only one replacement IUS is allowed per subject. Two insertion attempts are allowed as long as replacement criteria are met for both attempts. Replacement can occur only if all of the following conditions are met:

- Reinsertion occurs no more than 14 days after the expulsion;
- Reinsertion occurs at least 7 days prior to treatment Cycle 3 or Cycle 6;
- Reinsertion cannot occur during treatment Cycle 3 or Cycle 6.
- Pregnancy can reasonably be excluded

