5.4 Standard Calculations

Variables requiring calculation will be derived using the following formulas:

- **Study day** – For a given date (*date*) on or after successful IUS insertion (*iusindt*), study day is calculated as:

$$\text{Study day} = \text{date} - \text{iusindt} + 1$$

For a given date (*date*) prior to successful IUS insertion (*iusindt*) or for subjects with failed insertion, study day is calculated as:

$$\text{Study day} = \text{date} - \text{iusindt}.$$

The day of successful IUS insertion is Study Day 1 and the day prior to IUS insertion is Study Day -1. There is no Study Day 0

Months – A duration expressed in months is calculated as the number of completed calendar months plus the proportion of any partial month completed. A month is calculated using the following formula: Duration in months = $(\text{date2}-\text{date1})/30.4$

- **Years** - A duration expressed in years between one date (*date1*) and another later date (*date2*) is calculated using the formula noted below:

$$\text{Duration in years} = (\text{date2}-\text{date1})/365.25$$

- **Age** - Age is calculated as the number of years from the date of birth (*DOB*) to the IUS insertion attempt date (*iusindt*). For displaying a subject's age, the following formula is used:

$$\text{Age (years)} = \text{floor}(\text{insertion attempt date} - \text{birthdate})/365.25$$

- **Body Mass Index (BMI)** - BMI is calculated using height (in cm) and weight (in kg) at Screening Visit 1:

$$\text{BMI (kg/m}^2\text{)} = \text{weight (kg)} / [\text{height (cm)} / 100]^2$$

- **Cycles of Use** – Cycles are calculated using the date the IUS was expelled/removed (from the IUS Discontinuation CRF). Total use duration expressed as the number of 28-day cycles is defined as IUS expulsion/removal date or date of Visit 8 - date of

IUS insertion ($i_{usindt}+1)/28$. If re-insertion for expulsion takes place, the last IUS expulsion/removal date or date of Visit 8 is used. If the expulsion/removal date is unknown then:

- Subjects who are still on treatment will have their last known date of product use used in the cycle calculations in lieu of an IUS expulsion/removal date or date of Visit 8, derived as follows: The last known date of product use will be the last date of on-study contact with the subject where she reported that the IUS is still in place

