6. ANALYSIS POPULATIONS

The Safety population will include all subjects enrolled who underwent an IUS insertion attempt, regardless of outcome.

The following subject populations will be used for efficacy analyses:

- Modified-Intent-To-Treat (MITT): All subjects with qualifying baseline data at study entry for whom the IUS is successfully inserted and for whom there is at least one assessment of MBL during the Treatment Phase Cycle 3 or Cycle 6. All MBL values reported for both validated and unvalidated used feminine hygiene products will be included. This is the main population for the efficacy analyses.
- Supportive MITT: A supportive subset of the MITT population with baseline and post-baseline MBL data reported collected from only validated feminine hygiene products. This population is to demonstrate the robustness of the efficacy analyses.
- Per Protocol (PP): A subset of the MITT population that excludes subjects with major protocol deviations that are determined to have impact on the data of MBL assessment.

- Intent-to-Treat (ITT): All subjects with qualifying baseline data at study entry for whom the IUS is successfully inserted. This population is for evaluation of the sensitivity of results obtained from the MITT-based assessments. The baseline MBL will be carried forward (BOCF) for subjects who provide no Treatment Cycle 3 and no Treatment Cycle 6 data.
- Intent-to-Treat (ITT) Excluding Subjects LTFU and Subjects Who Withdraw Consent (WC) Without Study IUS Removal: All subjects with qualifying baseline data at study entry for whom the IUS is successfully inserted, excluding subjects who were LTFU or withdrew consent without study IUS removal and had no MBL assessment after baseline at Treatment Cycle 3 and Cycle 6. The baseline MBL will be carried forward (BOCF) for subjects who provide no Treatment Cycle 3 and no Treatment Cycle 6 data except for those subjects who were LTFU or withdrew consent without study IUS removal. This population is for evaluation of the sensitivity of results obtained from the MITT-based assessments.

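### SAP 11.6 bases expulsion rates on all insertion attempts, so women who never had an IUS placed dilute the crude rate and have no time origin for Kaplan-Meier

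*SAP*

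**What the plan says.** **Population.** SAP 11 sets the general rule: "All safety analyses will be based on the Safety population". SAP 6 defines that population: "The Safety population will include all subjects enrolled who underwent an IUS insertion attempt, regardless of outcome". For expulsions, SAP 11.6 repeats the choice: "Expulsion rates including analysis of complete and partial expulsions in the Safety Population will also be summarized". Protocol 9.9 likewise makes the Safety population the default for the other secondary outcomes, which include the cumulative continuation, expulsion and safety-removal rates at Visits 6, 7 and 8.

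**Timing.** SAP 11.6 defines event time as follows: "Time to event will be calculated as the date of continuation/expulsion/removal minus the date of IUS insertion plus one". For women with no event: "Subjects without a continuation/expulsion/removal will be censored at the last contact date", with a pointer to SAP 5.4.

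**Replacement.** Protocol 5.4 permits re-insertion after an expulsion under stated conditions, and "only one replacement IUS is allowed per subject". SAP 11.6 does not mention replacement. The SAP's one date rule for re-insertion is in the Cycles of Use item of SAP 5.4: "If re-insertion for expulsion takes place, the last IUS expulsion/removal date or date of Visit 8 is used".

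**The concern.** A rate of expulsion, continuation or removal has meaning only among women who have an IUS in place. The Safety population also holds women in whom placement failed. In a crude proportion they enlarge the denominator and can never add to the numerator.

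In the Kaplan-Meier analysis the problem is one of definition, because the clock starts at an insertion that did not happen. SAP 5.4 does not settle it. It uses one variable name for the successful insertion date (Study day) and for the insertion attempt date (Age), and it applies that variable to women with failed insertion. One programmer could drop these women and another could start their clock at the attempt. Protocol 6.8.2 requires no further follow-up after a failed insertion unless there are related adverse events. Women with such events are followed until resolution or stabilisation, so not all of them would leave the risk set at once.

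Expulsion is among the events that Protocol 7.3 singles out for specific monitoring. With few events expected, the rate should have one reproducible definition.

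**Working it through.** The documents state no planned expulsion rate for this trial and no number of failed insertions, so there is no figure of the plan to reproduce. What follows is illustrative.

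**Inputs**
- N = 100 women with an insertion attempt (planned enrolment, SAP 4).
- E = 4 women with an expulsion. This is an assumption, sized on the 3.9% first-year rate that Protocol 7.1.5 cites for women with heavy menstrual bleeding.
- f = 1 to 10 failed insertions (assumption).

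**1. Crude proportion.** I read the added summary in SAP 11.6 as a crude proportion. The Safety-based rate is E/N and the rate among women with an IUS placed is E/(N − f). The relative shortfall is 1 − (N − f)/N = f/N.

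| f | Safety-based | IUS placed | Difference (points) |
|---|---|---|---|
| 1 | 4/100 = 4.00% | 4/99 = 4.04% | 0.04 |
| 3 | 4.00% | 4/97 = 4.12% | 0.12 |
| 5 | 4.00% | 4/95 = 4.21% | 0.21 |
| 10 | 4.00% | 4/90 = 4.44% | 0.44 |

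**2. Kaplan-Meier at Day 168, f = 5.** Further assumptions: expulsions on Days 10, 30, 75 and 120; other losses of 5 women at Day 60 and 6 at Day 100.
- Women with an IUS placed (95): at risk 95, 94, 88 and 81. Estimate 1 − (94/95)(93/94)(87/88)(80/81) = 4.41%.
- Failed insertions added and censored at Day 1: they leave before the first event, so the estimate is the same 4.41%.
- Failed insertions kept to Day 31: at risk 100, 99, 88 and 81. Estimate 1 − (99/100)(98/99)(87/88)(80/81) = 4.31%.

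The Kaplan-Meier rate therefore depends on a censoring choice that the SAP does not state, but only by about 0.1 point in this example.

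**3. Does the timing rule cover a replaced IUS?** Take a woman who expels on Day 30 and is re-inserted on Day 35.
- Origin at the initial insertion (Day 1): 30 − 1 + 1 = 30 days, a usable event time.
- Origin at the replacement: 30 − 35 + 1 = −4 days, which is impossible.

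SAP 11.6 does not say which insertion date applies. The case is not remote. Reading Protocol 5.4 with Cycle 3 as Days 57–84 and Cycle 6 as Days 141–168, re-insertion is possible up to Day 50 and on Days 85–134. With the 14-day limit, an expulsion on Days 1–50 or 71–134 could be replaced: 50 + 64 = 114 of 168 days (68%).

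**The case against.** The strongest reply is that little changes. The pre-specified cumulative rate is Kaplan-Meier, and women without an IUS contribute essentially no time at risk. Only the supplementary crude summary is diluted, and by less than half a point even with 10 failures. The choice of population is stated openly. SAP 7.1 reports the number of successful insertions, so a reader can recompute the crude rate. The rates are descriptive and no efficacy decision rests on them. All of this stands and limits the point to a small correction. It does not make the denominator right. The SAP's own ITT and MITT populations already require a successful insertion, and its summary of duration of use is limited to women with at least one day of use.

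A reader might also infer that SAP 5.4, by taking the last expulsion or removal date, removes expulsions that were followed by replacement, and so could halve the reported rate. The documents do not support that. The rule belongs to the count of cycles used, an exposure measure. SAP 11.6 times an expulsion at its own date and cites SAP 5.4 only for censoring women without an event. Nothing says that a replaced expulsion is not counted. Expulsions should also appear through routes that do not use that end date, such as the adverse event tables and the number-and-percentage summaries of SAP 11.5. What remains is silence in SAP 11.6 about replacements, which calls for clarification.

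**Conclusion.** The denominator point holds as a small correction. As written, the crude expulsion rate is diluted by a relative amount equal to the share of failed insertions: 0.04 to 0.44 points on a rate of about 4% for an assumed 1 to 10 failures per 100. The Kaplan-Meier rate is unaffected if women with failed insertion are censored at Day 1, and moves by about 0.1 point if 5 such women stay in the risk set to Day 31. Their time origin is undefined in either case. The numbers of expulsions and failures, and their timing, are assumptions, and with no failed insertions the effect is zero.

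It would go too far to conclude that the trial's expulsion rate is understated in general. That would need the Kaplan-Meier rate to be biased, or replaced expulsions to be discarded, and the SAP prescribes neither.

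**What to change.** In SAP 11.6, base the expulsion, continuation and safety-related removal rates, both crude and Kaplan-Meier, on women with a successful IUS insertion.

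As clarification in the same paragraph, state that:
- time runs from the initial successful insertion;
- the expulsion event is the first confirmed complete or partial expulsion, whether or not the IUS is then replaced.

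No new reporting of insertion failures is needed, since SAP 11.5 already summarises them.

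The cost is a few lines of SAP text and no new data, because successful insertions are already counted under SAP 7.1. The downside for the sponsor is a crude expulsion rate that looks slightly less favourable.
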